#### 8.1.4 Compatibility

Compatible IV bag materials: PVC plasticized with DEHP, non-PVC (polyolefin), EVA, or PE lined polyolefin.

#### 8.1.5 Handling

Qualified personnel, familiar with procedures that minimize undue exposure to themselves and the environment, should undertake the preparation, handling, and safe disposal of the chemotherapeutic agent in a self-contained and protective environment.

#### 8.1.6 Availability

Pembrolizumab is an investigational agent and will be supplied free of charge from Merck.

#### 8.1.7 Preparation

Pembrolizumab solution for infusion must be diluted prior to administration. Allow the required number of vials to equilibrate to room temperature. Do not shake the vials. Do not use if opaque or extraneous particulate matter other than translucent to white proteinaceous particles is observed. Do not use if discolored. To prepare the infusion solution add the dose volume of Pembrolizumab to an infusion bag containing 0.9% Sodium Chloride Injection, USP or 5% Dextrose Injection, USP. Gently invert the bag 10-15 times to mix the solution. The final concentration must be between **1 mg/mL to 10 mg/mL**.

### **8.1.8 Administration**

Route of administration: IV infusion only. Do not administer as an IV push or bolus injection.

Method of administration: Infuse over approximately 30 minutes (range: 25-40 minutes) using an infusion set containing a low-protein binding 0.2 to 5 m in-line filter made of polyethersulfone or polysulfone. Infusion rate should not exceed 6.7 mL/min. A central line is not required however if a subject has a central venous catheter in place, it is recommended that it be used for the infusion. Do not co-administer drugs through the same infusion line. Following the infusion, flush the IV line with normal saline.

### **8.1.9 Ordering**

Pembrolizumab will be obtained directly from Merck, the study sponsor.

### **8.1.10 Accountability**

The investigator, or a responsible party designated by the investigator, should maintain a careful record of the inventory and disposition of the agent using the NCI Drug Accountability Record Form (DARF) or another comparable drug accountability form. (See the NCI Investigator's Handbook for Procedures for Drug Accountability and Storage.)

### **8.1.11 Destruction and Return**

At the end of the study, unused supplies of Pembrolizumab should be destroyed according to institutional policies. Destruction will be documented in the Drug Accountability Record Form.

[figure not shown]
## **8.2 Eribulin mesylate**

Please refer to the Investigator's Brochure for detailed agent information, and to the FDA label for additional information.

The chemical name for eribulin mesylate is 11,15:18,21:24,28-Triepoxy-7,9ethano-12,15-methano-9H,15H-furo[3,2-i]furo[2',3':5,6]pyrano[4,3-b][1,4]dioxacyclopentacosin-5(4H)-one,2[(2S)-3-amino-2-hydroxypropyl]hexacosahydro-3-methoxy-26-methyl-20,27-bis(methylene)-

(2R,3R,3aS,7R,8aS,9S,10aR,11S,12R,13aR,13bS,15S,18S,21S,24S,26R,28R,29aS)-methanesulfonate (salt). Its molecular weight is: 826.00.

Structural formula:

### 8.2.1 Form

Eribulin mesylate is a sterile, ready-to-use, clear, colorless aqueous solution for i.v. administration.

Eribulin mesylate for i.v. injection will be supplied on an open-label basis by the sponsor in single-use vials. Each single-use vial contains 1 mg/2 mL of clear, colorless solution. Each single-use vial of eribulin mesylate is primarily packaged in a 5 mL nominal volume United States Pharmacopeia (USP) Type 1 Flint glass, stoppered with a FluroTec® plug stopper and sealed with an aluminum seal and a flip-off cap. Twelve labeled vials of eribulin mesylate are packaged in a labeled carton. Each of the 6 eribulin mesylate vials within a given labeled carton may be assigned individually to 6 different subjects or to the same subject, as required by the study site or as clinical supply inventory demands.

### 8.2.2 Storage Conditions

Eribulin mesylate must be stored in accordance with labeled storage conditions. Intact and unopened vials must be stored at ambient room temperature. **Do NOT refrigerate or freeze.** Shelf-life surveillance of the intact vials is ongoing. The 0.5 mg/mL solution has been shown to be stable in syringes at ambient temperature and ambient lighting for up to 4 hours, or under refrigeration for up to 24 hours. The drug is also stable at concentrations ranging from 0.005 ng/mL to 0.2 mg/mL when diluted in normal saline (0.9% sodium chloride [NaCl]) and kept refrigerated in syringes or i.v. bags for up to 48 hours at ambient temperature and ambient lighting, or under refrigeration. It is not compatible with solutions with dextrose.

Product vials that are opened and refrigerated between 2°C to 8°C (36°F – 46°F) must be used within 24 hours of being opened, and the remaining drug solution discarded.

Temperature monitoring for eribulin mesylate is required at the storage location to ensure that the study drug is maintained within an established temperature range. The investigator is responsible for ensuring that the temperature is monitored throughout the total duration of the trial and that records are maintained; the temperature should be monitored continuously by using either an in-house validated data acquisition system, a mechanical recording device such as a calibrated chart recorder, or by manual means, such that minimum and maximum thermometric values over a specific time period can be recorded and retrieved as required.

### **8.2.3 Handling**

Qualified personnel, familiar with procedures that minimize undue exposure to themselves and the environment, should undertake the preparation, handling, and safe disposal of the eribulin mesylate in a self-contained and protective environment.

### **8.2.4 Availability**

Eribulin mesylate is being provided by Eisai for this trial.

### **8.2.5 Ordering**

Eribulin mesylate will be ordered directly from Eisai.

### **8.2.6 Treatment Compliance**

Eribulin mesylate will be administered by trained medical personnel at the investigational site. Treatment compliance will be monitored through drug accountability documentation, as well as the recording of study treatment administration in the subject's medical record. In addition, all details pertaining to the administration of eribulin mesylate, including but not limited to date, actual dose, and start and end times of each dose, will be recorded on the Study Drug Administration page of the subject's eCRF. Clinical research associates (CRAs) will review treatment compliance during investigational site visits conducted during and at the completion of the study.

### **8.2.7 Drug Supplies and Accountability**

Drug supplies and accountability will be as institutional policy.

The investigator, or a responsible party designated by the investigator, will maintain a careful record of the inventory and disposition of the agent (investigational or free of charge) using the NCI Drug Accountability Record or another comparable drug accountability form. (See the CTEP website at <http://ctep.cancer.gov/protocolDevelopment> for the "Policy and Guidelines for Accountability and Storage of Investigational Agents" or to obtain a copy of the drug accountability form.)

## **9. BIOMARKER, CORRELATIVE, AND SPECIAL STUDIES**

All patients will be asked to provide archival tumor tissue (either paraffin blocks or 20 unstained slides, ideally 4 micron thickness). However, if archival tissue is not available or not evaluable, that will not be a basis to exclude the patient from any portion of the trial or the planned analysis. Archival tissue will be used for immune profiling assays to ascertain baseline values in patients who choose not to undergo baseline research fresh tissue biopsy or in whom there is insufficient tissue or failed testing of any of the planned assays from baseline fresh tissue biopsy.

If obtained, we plan to use baseline biopsy tissue to perform a number of immune profiling assays, detailed below, and characterize the samples based on histology (TILs), protein

expression, and mRNA expression. Additionally, specimens we will banked for possible future analysis.

Serial blood draws for correlative science are required on this trial; blood draws will be obtained every 3 weeks on treatment days prior to the infusion of study drugs, at the end-of-treatment visit in patients who go off study for progressive disease, and all efforts will be made to obtain a sample at the time of progressive disease from participants who went off study for anything other than progressive disease. We will perform flow cytometry on these samples to characterize protein expression of immune mediators as detailed in the lab manual. Circulating tumor DNA will be assessed as well.

An optional research biopsy will be collected for participants who have consented and have biopsy accessible tumor on arm B crossing over to pembrolizumab therapy.

An optional research biopsy at the time of progression will be collected for participants who consent and have biopsy accessible tumor. These biopsies will undergo the same characterization testing as described for baseline biopsies.

All patients will additionally be asked to provide a stool sample at three separate timepoints: prior to treatment, during treatment, and at the time of disease progression. A fourth collection may be requested from patients who experience grade  $\geq 2$  diarrhea after discussion with the PI. This collection is not required, but is strongly encouraged. These samples will be analyzed for microbiota content.

Please refer to the separate laboratory manual for additional correlative details including collection, processing, and shipping instructions.

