- 3.1.11 Participants must have an archival tumor sample available (1 block or 20 unstained slides). If no archival tissue is available, participants must be willing to undergo a research biopsy of their disease if it is safely accessible.
- 3.1.12 Age  $\geq$  18 years of age
- 3.1.13 ECOG performance status  $\leq$ 2 (Karnofsky  $\geq$ 60%, see Appendix A)

3.1.14 Participants must have normal organ and marrow function as defined below:

- absolute neutrophil count	$\geq 1,500/\text{mcL}$
- platelets	$\geq 100,000/\text{mcL}$
- hemoglobin	$\geq 8 \text{ g/dL}$
- total bilirubin	$\leq 1.5 \times$ institutional upper limit of normal (ULN)
- AST(SGOT)/ALT(SGPT)	$\leq 2.5 \times$ institutional ULN ( $\leq 5 \times$ institutional ULN with documented liver metastases,
- serum creatinine	$\leq 1.5 \text{ mg/dL}$ or calculated GFR $\geq 60 \text{ mL/min}$
- INR/PT	$\leq 1.5$ times ULN unless participant is receiving anticoagulant therapy, as long as PT or PTT is within therapeutic range of intended use of anticoagulants
- aPTT/PTT	$\leq 1.5$ times ULN unless participant is receiving anticoagulant therapy, as long as PT or PTT is within therapeutic range of intended use of anticoagulants

3.1.15 The effects of eribulin mesylate and pembrolizumab on the developing human fetus are unknown. Pre-clinical data was suggestive of a teratogenic effect of eribulin mesylate. For these reasons women of child-bearing potential and men must agree to use adequate contraception (hormonal or barrier method of birth control; abstinence) for the duration of study participation and 4 months after the last dose of eribulin mesylate and/or pembrolizumab. Note: abstinence is acceptable if this is the usual lifestyle and preferred contraception for the subject.

- Should a woman become pregnant or suspect she is pregnant while she or her partner is participating in this study, the treating physician and principal investigator should be informed immediately.
- While on the study, women must not breastfeed.
- Subjects of childbearing potential are defined as those who have not been surgically sterilized and/or have had a menstrual period in the past year

3.1.16 Female subjects of childbearing potential, as defined above, must have a either a negative urine or a negative serum pregnancy test within seven (7) days of first dose of pembrolizumab. If a urine test is positive or cannot be confirmed as negative, a serum pregnancy test will be required.

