## 9.1 Summary table: research tissue and blood specimen collection

Research Sampling	Time point	Contents
Blood	Cycle 1 Day 1	1-9 mL Streck Tube 5- 10mL green top tubes*
	Every Cycle Day 1	5- 10mL green top tubes *
	Restaging Visits Only	1-9mL Streck Tube
	Off Treatment for PD	1-9mL Streck Tube 5- 10mL green top tubes*
	Time of PD, in patients who came off-study for a reason other than PD (Optional)	1-9mL Streck Tube 5- 10mL green top tubes*
Fresh Tissue	Pre-treatment (Optional) – within 7 days of starting therapy	5-7cores
	Progression**	5-7cores
Archival Tissue	Anytime	1 block or 20, 4 micron unstained slides

Stool Sample	Pre-treatment (within 28 days of starting therapy)	Home Stool Kit (DNA Genotek)
	Cycle 3 Day 1 (within 14 days prior)	
	Disease Progression	
	At the time of grade $\geq 2$ diarrhea (Optional)***	

\* EDTA (purple top) tubes or CPT tubes may be used interchangeably with green top tubes

\*\*Biopsy at the time of disease progression is optional for subjects on Arm A. Subjects on Arm B will be required to undergo a biopsy if they have accessible disease at the time of progression on Eribulin therapy, prior to initiating crossover treatment. Subjects on Arm B Crossover Therapy may choose to undergo an optional biopsy at the time of disease progression.

\*\*\* Collection at the time of grade  $\geq 2$  diarrhea is optional and should be discussed with the study PI.

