## **9.6 Hypothesis for correlative objectives**

### **9.6.1 Hypotheses**

- We hypothesize that the immune marker profile in the peripheral blood will change over the course of eribulin mesylate +/- pembrolizumab therapy.
- We hypothesize that a larger increase in markers of immune activity in the peripheral blood will correlate with a better disease response as assessed on concurrent restaging scans, and in terms of best radiographic response at any time on trial.  
We hypothesize that an immune marker or composite of markers in the peripheral blood at baseline will correspond to TIL percentage in archival tumor tissue.
- We hypothesize that the immune activity associated with a breast tumor, as assessed both in tumor tissue and in circulating blood, will be less at the time of disease progression on therapy compared to the time of therapy initiation.
- We hypothesize that the structure and function of the gut microbiome differs among patients with breast cancer.
- We hypothesize that the structure and function of the gut microbiome before starting pembrolizumab and eribulin can be predictive of efficacy of this therapy, with a greater microbial diversity, estimated by Shannon index, being predictive of efficacy.
- We hypothesize that the structure and function of gut microbiome changes in response pembrolizumab-based therapy and can predict the likelihood of response to pembrolizumab.
- We hypothesize that the abundance and functional profile of specific gut bacteria is associated with response to pembrolizumab.

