### **13.6.1 *Blood and tissue correlative science endpoints:***

- We will describe the presence and abundance of multiple immune markers in metastatic HR-positive breast tumors (characterization will be based on histology, protein

expression, and mRNA expression; see Section 9 for further details on characterization) using frequency tables and descriptive statistics (mean, standard deviation, median, and inter-quartile range).

- We will explore the correlation of immunosuppressive and/or immune-stimulating immune marker profiles at baseline to disease response to therapy (response assessed by RECIST 1.1 and irRECIST criteria) using odds ratios and 95% confidence intervals.
- We will summarize serial changes in immune marker profile in peripheral blood mononuclear cells (PBMCs) from baseline (pre-trial therapy) using mean, standard deviation, median, and inter-quartile range.
- We will plot serial changes in the immunosuppressive and/or immune-stimulating immune marker profile in PBMCs by disease response to therapy (response assessed by RECIST 1.1 and irRECIST criteria)
- We will explore an immune marker or set of markers in circulating PBMCs that corresponds to tumor infiltrating lymphocyte (TIL) percentage in baseline tumor
- In the cohort of patients who have re-biopsy at progressive disease (PD): We will summarize changes in a broad array of immune markers from baseline to time of progressive disease on trial therapy using mean, standard deviation, median, and inter-quartile range.

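### Section 13.6.1 summarizes tissue immune-marker change to progression without separating fresh from archival baselines, so archival pairs do not show change from the start of trial therapy

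*Combined protocol and SAP*

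**What the plan says.** **Source of the baseline.** Section 9: "Archival tissue will be used for immune profiling assays to ascertain baseline values" in patients who decline the fresh baseline biopsy. The same rule applies where there is "insufficient tissue or failed testing of any of the planned assays from baseline fresh tissue biopsy". Substitution can therefore happen assay by assay, and one patient can have a fresh baseline for one marker and an archival baseline for another.

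**Timing.** The Section 9.1 table lists fresh tissue as "Pre-treatment (Optional) – within 7 days of starting therapy". For archival tissue the time point is given as *Anytime*. Sections 3.1.11, 9 and 9.1 and study calendar note l specify the amount of archival tissue (one block or 20 slides) but not its age, its site or the therapy given since.

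**Analysis.** Section 13.6.1, for patients re-biopsied at progression: "We will summarize changes in a broad array of immune markers from baseline to time of progressive disease on trial therapy", by mean, SD, median and inter-quartile range. It gives no split by baseline source, no restriction to fresh pairs and no sensitivity analysis.

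**Hypotheses (Section 9.6.1).** Tumor immune activity, measured in tissue and in circulating blood, "will be less at the time of disease progression on therapy compared to the time of therapy initiation". Separately, a marker or set of markers "in the peripheral blood at baseline will correspond to TIL percentage in archival tumor tissue". For that second question, objective 1.4.5 and Section 13.6.1 name the baseline tumor instead.

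**Status.** Section 13.6 declares all correlative analyses exploratory and hypothesis-generating.

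**The concern.** The change summary is meant to describe what happens to the tumor immune profile between the start of trial therapy and progression. An archival block need not show the state at the start. Section 3.1.1 accepts metastasis shown by examination or imaging alone, so the block can be the primary tumor. Section 3.1.5 allows up to two prior chemotherapy lines in the metastatic setting, and Section 3.1.4 anticipates prior hormonal therapy, so the block can predate several treatments.

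The protocol itself gives reasons to expect that this matters. Section 2.5 says that taxanes given before surgery raise TILs and that paclitaxel upregulates PD-L1 on breast cancer cells. Section 2.6.1 says that less is known about the immune profile of metastatic disease than about the adjuvant and neoadjuvant settings.

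At stake is whether a difference that arose before enrollment is described as change on trial therapy and carried forward as a lead for the future studies that Section 13.6 foresees. The blood-TIL question has a different problem: blood drawn at baseline may be set against tissue of another date and site, and the plan names the tissue in two ways.

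**Working it through.** The plan states no figure for either analysis, so there is nothing to reproduce. The check is a comparison of sections, followed by an illustration.

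**1. What an archival pair measures.** For one patient and one marker, let A be the archival value, C the value at therapy start and P the value at progression.
- Fresh pair: P − C, the change from therapy initiation.
- Archival pair: P − A = (P − C) + (C − A).

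The extra term, C − A, arises before the first dose and reflects time, site and intervening therapy.

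**2. Effect on a summary of all pairs.** Let f be the share of pairs with an archival baseline and s the mean of C − A in those pairs. Then

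observed mean change = true mean change + f × s.

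The documents give neither f nor s. Assume a true change of zero, f from 0.25 to 1, and |s| from 0.25 to 0.5 SD of the change:
- smallest: 0.25 × 0.25 = 0.0625 SD
- largest: 1 × 0.5 = 0.50 SD

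Either can be positive or negative.

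**3. What a reader of the table might conclude.** The plan proposes no test, but a reader can form an interval from a mean and an SD. In simulation with zero true change and SD 1, a nominal 95% t interval should exclude zero 5% of the time. It does so as follows (the numbers of pairs are assumptions):

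| Pairs | f | abs(s) = 0.25 SD | abs(s) = 0.5 SD |
|---|---|---|---|
| 20 | 0.5 | 8% | 18% |
| 20 | 1 | 18% | 56% |
| 30 | 0.5 | 10% | 25% |
| 30 | 1 | 26% | 75% |

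**4. Is f likely to be negligible?** No figure is given, but the structure suggests not. Section 3.1.11 and calendar note l call for a baseline biopsy only when archival tissue is unavailable; otherwise it is optional. Sections 3.4.4 and 9.2.1 and calendar note k require a biopsy of accessible disease before Arm B patients cross over, although the opening of Section 9 calls it optional. Section 13.5 assumes about 30 crossovers. A required progression biopsy set against an optional baseline biopsy will tend to create archival pairs, perhaps more of them in Arm B. That is inference.

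**5. Which assays are exposed.** TILs for flow cytometry are isolated from biopsy tissue (Sections 9.2.1 and 9.7.3, Appendix G), which a block or slides cannot supply. The problem is confined to assays that archival material can support, such as TIL percentage and immunohistochemistry. The blood part of the progression hypothesis is sampled at Cycle 1 Day 1 and at progression and is not affected.

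**6. Blood-TIL correlation.** Let ρ be the correlation of baseline blood with current TIL percentage, and r that of archival with current TIL percentage. If archival TIL relates to blood only through current TIL, and the sources have equal means and variances, the observed correlation is ρ × (1 − f + f × r), where f is now the share of TIL values that are archival. With an assumed ρ = 0.5:
- all archival (f = 1): r = 0.3 gives 0.15; r = 0.9 gives 0.45
- half archival (f = 0.5): r = 0.3 gives 0.325; r = 0.9 gives 0.475

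**The case against.** Much can be said for the plan. These analyses are exploratory, the change summary is descriptive, and no primary or secondary endpoint depends on it. Section 9.7 lets the correlative analyses be altered, and the laboratory manual, which is not in the documents, may set specimen rules. All of this limits the importance of the point. None of it supplies the missing separation by source in 13.6.1.

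A reader might infer four stronger claims. The documents do not support them.

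- **That the plan pools fresh and archival pairs.** Section 13.6.1 is silent on this. Its term re-biopsy could even be read to imply an earlier trial biopsy. But Section 9 expressly lets archival tissue supply the baseline, and nothing keeps the two apart.
- **That *Anytime* permits tissue of any age.** In a specimen-collection table it may mean when the block may be submitted. The point rests instead on the absence of an age limit anywhere in the documents.
- **That the result is biased toward the hypothesis of lower immune activity at progression.** This requires archival tissue to be richer in immune markers, which no section says. Section 2.5 on taxanes points the other way: tissue taken before chemotherapy could be lower in TILs, which would hide a fall.
- **That the blood-TIL analysis also departs from its hypothesis or reports a false change.** It is a correlation and reports no change, and Section 9.6.1 names archival tissue as its comparator. The fault there is the conflict with objective 1.4.5 and Section 13.6.1, and the possible mismatch in date and site.

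It can also be objected that a fresh-only analysis has a selection problem of its own. That stands, and it is a reason to report both sources rather than discard one.

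**Conclusion.** The point holds within limits. Followed as written, Sections 9 and 13.6.1 allow differences that predate the trial to be reported as change on trial therapy in every pair whose baseline is archival. For those pairs the summary does not measure change from therapy initiation.

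Sign and size are unknown. The 0.06 to 0.50 SD range, the interval error rates and the attenuated correlations rest on assumed values of f, s, ρ, r and the number of pairs, and should be read only as showing that the effect need not be small. If nearly all pairs have fresh baselines, it is negligible.

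The PFS comparison, the secondary endpoints, the safety analyses and the blood-marker series are untouched. The correction is worth making because it is cheap and because these results are meant to guide later studies.

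**What to change.** **Section 13.6.1, tissue change.** Report paired change from baseline to progression separately by baseline source, assigned marker by marker, with the number of pairs in each group. Base any statement about change on trial therapy on pairs with a fresh biopsy within 7 days before therapy. Show archival-baseline pairs apart, labelled by primary or metastatic site, collection date and intervening therapy.

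**Blood-TIL analysis.** Reconcile Section 9.6.1 (archival tissue) with objective 1.4.5 and Section 13.6.1 (baseline tumor), so that one tissue is named throughout, and report the correlation by specimen source.

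**Cost.** SAP wording and a few data fields: archival collection date, site, and therapy between collection and first dose. No new procedure is needed. The fresh-baseline summary will have fewer pairs, and those patients are selected for accessible disease and for consent to an optional biopsy. The report should say so.
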